4.2.1 Inclusion and Exclusion Criteria for Adult Participants

4.2.1.1 Inclusion and Exclusion Criteria for Adult Stage 1

4.2.1.1.1 Inclusion Criteria for Adult Stage 1

Individuals who meet all of the following criteria are eligible for randomization/allocation as study participants in Adult Stage 1:

1. Individuals 18 years of age or older that meet classification criteria for SLE, SSc, RA, MS, or pemphigus.
2. Participants must meet the 2019 American College of Rheumatology/European League Against Rheumatism (ACR/EULAR) [2] or 2012 Systemic Lupus International Collaborating Clinics (SLICC) classification criteria for SLE [3], the 2010 ACR/EULAR classification criteria for RA [4], the 2013 EULAR/ACR classification criteria for SSc [5], the 2017 McDonald [6] criteria for MS, and the international consensus criteria for pemphigus [7].
 - a. If a participant has been diagnosed with more than one autoimmune disease, the participant will be assessed based on the disease that is selected for study entry.
3. Willing and able to sign informed consent.
4. Documented full COVID-19 vaccination (CDC card or documentation in medical records) that was completed at least 4 weeks prior and no more than 52 weeks prior to the Screening visit.
5. Negative or suboptimal serologic response to initial COVID-19 vaccine regimen, defined as an Elecsys® Anti-SARS-CoV-2 S result ≤ 200 U/mL, at Screening visit.
 - a. Initial COVID-19 vaccine regimen is defined as either:
 - i. 2 doses of the Pfizer-BioNTech COVID-19 Vaccine
 - ii. 2 doses of the Moderna COVID-19 Vaccine
6. Must be currently taking one of the following IS medications with or without additional disease-related medications: MMF (minimum of 1000 mg per day)/MPA (minimum of 720 mg per day), MTX (minimum of 7.5mg per week), or B cell depleting agents within the past 18 months (such as rituximab, ocrelizumab, or ofatumumab).

- a. If taking MMF/MPA or MTX, the participant must have initiated therapy at least 8 weeks prior to randomization and be taking the same medications (regardless of dose) as at the time of the initial COVID-19 vaccine regimen. Note: Participants who withheld their IS medications around their initial vaccinations are eligible to participate.
- b. If enrolling in the BCDT cohort, the participant must have received an anti-CD20 or an anti-CD19 BCDT in the past 18 months.

7. No changes in background IS medications, including MMF/MPA or MTX, in the 4 weeks prior to Screening, excluding the following:

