4.2.2 Inclusion and Exclusion Criteria for Pediatric Participants

4.2.2.1 Inclusion and Exclusion Criteria for Pediatric Stage 1

4.2.2.1.1 Inclusion Criteria for Pediatric Stage 1

Individuals who meet all of the following criteria are eligible for enrollment randomization/allocation as participants in Pediatric Stage 1:

1. Individuals 2-17 years of age that meet classification criteria for SLE, JIA, POMS, or JDM. Note: Juvenile idiopathic arthritis includes the following conditions: polyarticular JIA (both RF + and -), oligoarticular persistent and oligoarticular extended JIA, psoriatic arthritis, and enthesitis related JIA.

- a. Participants must meet the 2017 EULAR/ACR classification criteria for adult and juvenile idiopathic inflammatory myopathies and their major subgroups [8], the International League of Associations for Rheumatology (ILAR) classification for JIA [4], the 2017 McDonald [6] criteria for MS, or the Bohan and Peter criteria or the 2017 EULAR/ACR classification criteria for JDM.
- b. If a participant has been diagnosed with more than one autoimmune disease, the participant will be assessed based on the disease that is selected for study entry.

2. Parents/guardians of all pediatric participants and participants ages 14 – 17 must be willing and able to sign informed consent. Participants ages 7-13 must be willing and able to sign assent.
3. Documented EUA-authorized or FDA-approved COVID-19 vaccine doses (CDC card or documentation in medical records) that was completed at least 4 weeks prior and no more than 52 weeks prior to the Screening visit.
4. Negative or suboptimal serologic response to initial EUA-authorized or FDA-approved COVID-19 vaccine doses, defined as an Elecsys® Anti-SARS-CoV-2 S result ≤ 200 U/mL, or a low immune response, defined as an Elecsys® Anti-SARS-CoV-2 S (RBD) result of ≤ 2500 U/mL, within 4 weeks of the Stage 1 Baseline/Week 0 visit.
 - a. Initial COVID-19 vaccine regimen is defined as:
 - i. Pfizer-BioNTech COVID-19 Vaccine (2 through 4 years of age): 3 age-appropriate doses.
 - ii. Pfizer-BioNTech COVID-19 Vaccine (5 through 17 years of age): 2 age-appropriate doses.
 - iii. Moderna COVID-19 Vaccine (2 through 17 years of age): 2 age-appropriate doses.

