13.4.3 Supportive Analyses of the Primary Endpoint

Supportive analyses will also use a multivariable regression model on the entire vaccinated population in order to estimate the rates of vaccine response within and across arms (age group, cohort, vaccine, and IS treatment plan group) using the logistic link function, and including baseline covariates for disease type (SLE, RA, MS, SSc, and pemphigus in adults and JIA, pediatric SLE, JDM, and POMS in pediatrics) and immune response to the initial COVID-19 vaccine regimen (anti-COVID-19 antibody negative or positive). Descriptive statistics will be used to summarize antibody response to the additional homologous vaccine dose on a continuous scale. Estimates of the average antibody response and variance within and across cohorts will be obtained from a multivariate general linear regression model. Based on published data on the assays, it is anticipated that log-transformation of assay values will allow for Gaussian assumptions to hold, but alternative Box-Cox transformations of the data may be explored to stabilize the variance.

The primary and supportive analyses will also be replicated on the Per-protocol population and using alternative strategies for missing data.

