13.4.4 Analyses of Secondary and Other Endpoint(s)

For Stage 1, the multivariable logistic and linear regression models defined in Section 13.4.3 Supportive Analyses of the Primary Endpoint above will be used to compare response to additional homologous doses of COVID-19 vaccine for a variety of subgroups. Appropriate contrasts will be defined to compare vaccine response for the following:

- Continuing versus withholding IS medications will be compared within cohort (cohorts A and B only) and within and across type of vaccine.
- The types of additional vaccine dose administered will be compared within cohorts and across cohorts, and within and across IS treatment plan groups.
- Type of IS medications will be compared within and across each type of vaccine.
- Age groups and type of disease will be compared within and across each type of vaccine.
- Corticosteroid dose at baseline will be added as a covariate to the model to assess impact on vaccine response.
- Immune response to the initial COVID-19 vaccine regimen will be assessed within and across each type of vaccine.
- Additional covariates for disease activity, co-morbid illness, age, and sex may be added to assess whether the clinical parameters are associated with response to additional vaccine dose.

Data for the Moderna COVID-19 Vaccine and Pfizer-BioNTech COVID-19 Vaccine may be combined in the comparisons above to assess the effect of mRNA vaccines together.

The incidence of seroconversion following additional vaccine doses of COVID-19 vaccine will be evaluated in the subgroups of participants that are anti-COVID-19 antibody negative at baseline using separately, (a) NIAID-VRC MSD 3 plex (Wu-1 full-length spike, RBD, and N proteins) assay with thresholds <1204.7 , 517.9 , and 9779.6 AU/mL, respectively, and (b) the Roche Elecsys® Anti-SARS-CoV-2 S electrochemiluminescence immunoassay with a threshold <0.80 U/mL. The proportions who seroconvert within and across arms will be summarized using 95% Clopper-Pearson confidence intervals, and comparisons will use a two-sample Binomial exact test with nominal two-sided alpha = 0.05.

For the subgroups of participants that are anti-COVID-19 antibody positive at baseline using separately, (a) the NIAID-VRC MSD 3 plex (Wu-1 full-length spike, RBD, and N proteins) assay, and (b) the Roche Elecsys® Anti-SARS-CoV-2 S electrochemiluminescence immunoassay with a threshold ≥ 0.80 U/mL. Fold improvement for each assay will be defined as:

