4. GENERAL ANALYSIS AND REPORTING CONVENTIONS

The following is a list of general analysis and reporting conventions to be applied for this study:

- Categorical variables will be summarized using counts (n) and percents (%) and will be presented in the form n (%).
- Moment statistics including mean will be reported at 1 more significant digit than the precision of the original data. The standard deviation will be reported at 2 more significant digits than the precision of the original data. The level of precision may be modified on specific displays based on clinical judgement.
- Order statistics including median, min, and max will be reported to the same level of precision as the original observations. If any values are calculated to have more significant digits, then the value should be rounded so that it is the same level of precision as the original data.
- Following SAS default rules, the median will be reported as the average of the two middle numbers if the dataset contains an even number of observations.
- Test statistics including t and z test statistics will be reported to two decimal places.
- P-values will be reported to 3 decimal places if greater than 0.001; if less than 0.001, then they will be reported as ‘<0.001’. P-values and significant levels will be reported as 0.05 rather than .05. A p-value will be reported as “1.000” only if it is exactly 1.000 without rounding. A p-value will be reported as “0.000” only if it is exactly 0.000 without rounding.
- No preliminary rounding should be performed; rounding should only occur after analysis. To round, consider the digit to the right of last significant digit; if <5 then round down, and if ≥ 5 then round up.
- In general, listings will be displayed by treatment arm and subject and will be sorted in the order that columns are displayed, starting with the first column on the left.
- All analyses will be performed using the SAS System version 9.4 or higher.

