8.2.4. Secondary Analyses of the Primary Endpoint

Descriptive statistics will be used to summarize antibody response to the additional homologous vaccine dose on a continuous scale, including median, minimum, and maximum, interquartile range, geometric mean, CV of the geometric mean, and 95% confidence intervals. Summary statistics, including 25th percentile, mean, median, and 75th percentile, will be plotted for each visit by treatment arm. Geometric mean and CV of the geometric mean will be computed as follows:

$$\text{Geometric mean} = \exp(\text{mean on } \log_e \text{ scale}).$$

$$\% \text{CV geometric mean} = \sqrt{\exp((SD \text{ on } \log_e \text{ scale})^2) - 1} \times 100$$

Primary and secondary analyses will be repeated for the RBD proteins to summarize antibody response to the additional homologous vaccine dose on a continuous scale. Supportive analyses will use descriptive statistics to summarize N protein levels as evidence of COVID infection.

In the final analysis, supportive analyses will also use a multivariable regression model on the entire vaccinated population in order to estimate the rates of vaccine response within and across arms (age group, cohort, vaccine, and IS treatment plan group) using the logistic link function, and including baseline covariates for disease type (SLE, RA, MS, SSc, and pemphigus in adults

and JIA, pediatric SLE, JDM, and POMS in pediatrics) and immune response to the initial COVID-19 vaccine regimen (anti-COVID-19 antibody negative or positive).

Estimates of the average antibody response and variance within and across cohorts will be obtained from a multivariate general linear regression model. Based on published data on the assays, it is anticipated that log-transformation of assay values will allow for Gaussian assumptions to hold, but alternative Box-Cox transformations of the data may be explored to stabilize the variance.

The primary and supportive analyses will also be replicated on the Per protocol population and using alternative strategies for missing data. Additional analysis details will be provided in subsequent versions of the SAP.

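### The supportive model cannot deliver a disease-adjusted adult-versus-pediatric comparison, because none of its nine disease labels occurs in both age groups

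*Protocol*

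**What the plan says.** Protocol 13.4.3 plans a "multivariable regression model on the entire vaccinated population" with a logit link, and a linear counterpart for antibody level. Age group is one of the factors that define an arm. The baseline covariates are prior immune response and disease type, the latter given as "including baseline covariates for disease type (SLE, RA, MS, SSc, and pemphigus in adults and JIA, pediatric SLE, JDM, and POMS in pediatrics".

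Protocol 13.4.4 draws its comparisons from these models: "For Stage 1, the multivariable logistic and linear regression models defined in Section 13.4.3" are to supply the contrasts, and one of them is that "Age groups and type of disease will be compared within and across each type of vaccine". The same section repeats the plan for Stage 2.

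SAP 8.2.4 carries the model over almost unchanged. It is to "estimate the rates of vaccine response within and across arms (age group, cohort, vaccine, and IS treatment plan group"), again on the whole vaccinated population and with the same two lists of diseases. Neither document says whether adult and pediatric SLE, or MS and POMS, share a level. Neither says whether disease is nested in age group, or over which mix of diseases a rate is averaged.

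**The concern.** A covariate can be adjusted for in a comparison of two groups only if some of its values occur in both. Here the disease lists do not overlap. Once a participant's disease label is known, the age group is known, so the pediatric indicator is the sum of the four pediatric disease indicators. The model cannot tell an effect of being a child from an effect of having one of the pediatric diseases.

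At stake is one planned secondary comparison. As specified it has no disease-adjusted answer, and a choice of coding or averaging made after open-label data are in hand would decide what is reported under that name.

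**Working it through.** **The plan's own figure.** The documents give no figure for the age contrast. The figure in Protocol 13.7 for comparing two single arms with this model is 80% power with 33 per arm at an odds ratio of 4.2. The odds ratio is (0.584/0.416)/(0.25/0.75) = 4.21, and the two-proportion power at two-sided 0.05 (alpha assumed, not stated there) is 0.800. It reproduces and does not bear on this point.

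**Inputs.**
- Adult diseases: "Individuals 18 years of age or older that meet classification criteria for SLE, SSc, RA, MS, or pemphigus" (Protocol 4.2.1), five labels.
- Pediatric diseases: "Individuals 2-17 years of age that meet classification criteria for SLE, JIA, POMS, or JDM" (Protocol 4.2.2), four labels. The model text in 13.4.3 names the first of these pediatric SLE.
- Stage 1 mRNA arms: ten adult (Protocol Table 2) and ten pediatric (Table 7).
- Prior immune response: two levels (13.4.3).
- Assumptions: an additive model; every arm contains every disease of its age group at both response levels; treatment plan coded withhold or not, with Cohort C as not withholding.

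**Rule.** A contrast is estimable if and only if its coefficient vector lies in the row space of the design matrix.

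**Main effects, nine disease labels.** Columns: intercept 1 + age 1 + cohort 2 + vaccine 1 + plan 1 + disease 8 + prior response 1 = 15. Rank 14. The missing rank is the identity between the pediatric indicator and the sum of the pediatric disease indicators. The age coefficient is not estimable; withhold versus continue is.

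**One term per arm, nine labels.**
- mRNA arms only: 1 + 19 + 8 + 1 = 29 columns, rank 28.
- With the adult Janssen arms (15 adult and 10 pediatric arms): 1 + 24 + 8 + 1 = 34 columns, rank 33.

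There is exactly one redundancy in each. The consequences are:

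| Quantity | Estimable? |
|---|---|
| Arm A1P minus arm A1, disease held fixed | No |
| Arm A1 rate averaged over all nine diseases | No |
| Arm A1 rate at any one adult disease | Yes |
| Arm A1 rate averaged over the five adult diseases | Yes |
| Arm A4 minus A1, and A4P minus A1P (withhold minus continue) | Yes |
| Pediatric average over its four diseases minus adult average over its five | Yes, but not adjusted for disease |

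**Shared levels.** Coding SLE with pediatric SLE and MS with POMS leaves seven levels: 1 + 1 + 2 + 1 + 1 + 6 + 1 = 13 columns, rank 13, and the age effect is estimable with everyone included. With one term per arm and all 25 arms: 1 + 24 + 6 + 1 = 32 columns, rank 32.

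**What identifies the age effect.** Removing both shared families leaves RA, SSc and pemphigus in adults and JIA and JDM in children, which are again disjoint: 1 + 1 + 2 + 1 + 1 + 4 + 1 = 11 columns, rank 10, age not estimable. The age effect therefore comes only from SLE and MS.

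**Separate models by age group, all Stage 1 arms.** Adult 1 + 14 + 4 + 1 = 20 columns, rank 20; pediatric 1 + 9 + 3 + 1 = 14 columns, rank 14. Both are full rank, but neither contains an age contrast.

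**The case against.** The strongest reply is that the documents do not fix the coding. Pediatric eligibility uses the plain label SLE, and POMS is assessed with the MS relapse definition, so shared levels may be intended. SAP section 5 defines its analysis samples by stage and age group, so the whole vaccinated population in SAP 8.2.4 might mean one age group at a time. The SAP takes precedence over the protocol (SAP section 2), defers subgroup details (8.5), and must be final before database lock. Protocol 13.4.4 also does not say that disease is held fixed in the age comparison.

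Part of this stands. The rank deficiency depends on taking the nine labels as nine levels of one combined model. But SAP 8.2.4 still lists age group among the arm factors, which has no role in an age-specific model, and separate models would leave the age comparison of 13.4.4 without a source. No text maps the adult and pediatric labels to each other. The deferral in 8.5 does not change the model already stated in 8.2.4. Each of these readings needs a sentence the plan does not contain.

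A reader might infer that all disease-adjusted arm rates are lost. They are not: they fail only when averaged over all nine diseases, which would assign adult diseases to children and the reverse, and no section asks for that. A reader might also infer that any age result would depend on the order of the labels. That assumes a particular software default. The SAP says only "All analyses will be performed using the SAS System version 9.4 or higher", and the difference between own-disease averages is estimable under any coding.

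**Conclusion.** With disease coded as listed, the disease-adjusted adult-versus-pediatric comparison is not estimable: 15 columns, rank 14. This is structural. Eligibility creates it, and no sample size removes it. Empty arm-by-disease cells in the real data could not restore the missing rank.

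The reach is narrow. Rates over an age group's own diseases and within-age contrasts stand. The primary analysis is an exact binomial test in each arm and does not use this model. SAP 8.1.4 treats all secondary analyses as exploratory, with descriptive p-values. A reader might rank this as a defect that must be repaired before the trial can be interpreted; for one exploratory comparison the documents do not support that. Severity is minor to moderate.

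**What to change.** Amend Protocol 13.4.3 and SAP 8.2.4 in two places.

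1. Estimate adjusted arm rates and within-age contrasts with disease nested in age group, or in separate adult and pediatric models. Average each arm's rate only over the diseases of its own age group, and state the weights.
2. For the age-group contrast in 13.4.4, fit a combined model in which SLE with pediatric SLE, and MS with POMS, are shared disease levels. Report that the disease-adjusted age effect is identified only through those families, and assumes that it is the same across diseases on the model's scale.

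No participants need be dropped: SSc, pemphigus and JDM can stay in as levels of one age group. Pairing RA with JIA is optional and not needed for estimability. If an age difference unadjusted for disease is what is wanted, the plan should say so.

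The cost is a few sentences and one extra model fit. The downside is that the age contrast rests on SLE and MS. It will be imprecise if those diseases are few in either age group, and unavailable if neither occurs in both.

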13.4.4 Analyses of Secondary and Other Endpoint(s)

For Stage 1, the multivariable logistic and linear regression models defined in Section 13.4.3 Supportive Analyses of the Primary Endpoint above will be used to compare response to additional homologous doses of COVID-19 vaccine for a variety of subgroups. Appropriate contrasts will be defined to compare vaccine response for the following:

- Continuing versus withholding IS medications will be compared within cohort (cohorts A and B only) and within and across type of vaccine.
- The types of additional vaccine dose administered will be compared within cohorts and across cohorts, and within and across IS treatment plan groups.
- Type of IS medications will be compared within and across each type of vaccine.
- Age groups and type of disease will be compared within and across each type of vaccine.
- Corticosteroid dose at baseline will be added as a covariate to the model to assess impact on vaccine response.
- Immune response to the initial COVID-19 vaccine regimen will be assessed within and across each type of vaccine.
- Additional covariates for disease activity, co-morbid illness, age, and sex may be added to assess whether the clinical parameters are associated with response to additional vaccine dose.

Data for the Moderna COVID-19 Vaccine and Pfizer-BioNTech COVID-19 Vaccine may be combined in the comparisons above to assess the effect of mRNA vaccines together.

The incidence of seroconversion following additional vaccine doses of COVID-19 vaccine will be evaluated in the subgroups of participants that are anti-COVID-19 antibody negative at baseline using separately, (a) NIAID-VRC MSD 3 plex (Wu-1 full-length spike, RBD, and N proteins) assay with thresholds <1204.7 , 517.9 , and 9779.6 AU/mL, respectively, and (b) the Roche Elecsys® Anti-SARS-CoV-2 S electrochemiluminescence immunoassay with a threshold <0.80 U/mL. The proportions who seroconvert within and across arms will be summarized using 95% Clopper-Pearson confidence intervals, and comparisons will use a two-sample Binomial exact test with nominal two-sided alpha = 0.05.

For the subgroups of participants that are anti-COVID-19 antibody positive at baseline using separately, (a) the NIAID-VRC MSD 3 plex (Wu-1 full-length spike, RBD, and N proteins) assay, and (b) the Roche Elecsys® Anti-SARS-CoV-2 S electrochemiluminescence immunoassay with a threshold ≥ 0.80 U/mL. Fold improvement for each assay will be defined as:

$$\text{Fold improvement} = \frac{\text{anti-COVID-19 Antibody Response Week 4}}{\text{anti-COVID-19 Antibody Response Baseline}}$$

Longitudinal changes in the anti-COVID-19 antibodies will be summarized over time by study visit using descriptive statistics. Details on handling missing data and intercurrent events, which result in anti-COVID-19 antibody response data being unevaluable for immune response, will be outlined in the statistical analysis plan.

Longitudinal changes in neutralization and pseudoneutralization assays will be summarized by study visit using descriptive statistics. For secondary continuous efficacy endpoints, descriptive statistics will be used to summarize the distribution of scores in each arm; for adult participants, this will include the H-SLEDAI (SLE participants), Tender/Swollen Joint Count (RA participants), PDAI (pemphigus participants), modified Rodnan Skin Score (SSc participants), CGI-C, PtGA, PGI-C, PGA, and PROMIS 29, and for pediatric participants, this will include the SLEDAI-2K (SLE), Tender/Swollen Joint Count (JIA participants), MMT-8 and CMAS (JDM participants), CGI-C, PtGA, PGI-C, PGA, and PedsQL. The proportion of participants who meet definition for disease-specific flares, including the Thanou modified SELENA-SLEDAI Flare Index (SLE participants), patient-reported flare assessment (SSc participants), and physician-assessed relapse (MS participants), will be summarized. The disease-specific flare endpoints will include Thanou modified SELENA-SLEDAI Flare Index (SLE participants), DAS28-CRP (RA participants), patient-reported flare assessment (SSc participants), flare assessment (pemphigus participants) and physician-assessed relapse (MS participants) in adults and the ACR Provisional Criteria for Global Flare in Childhood-onset SLE (for SLEDAI; pediatric SLE participants), physician-assessed relapse (POMS participants), and flare assessment (JDM participants).

Descriptive statistics will be used to summarize the proportions of participants in the safety arm who experience safety endpoints.

For Stage 2, analysis plans for primary and secondary endpoints will be repeated to evaluate the immune response to a subsequent alternative COVID-19 vaccine dose and to determine whether immunologic variables are associated with increased disease activity.

